**4.5. List exclusion criteria**

Focus Group Discussions

S/No	Group	Exclusion Criteria
1	TBA delivery clients	First pregnancy before 42 days of culmination; unwilling to participate in study; was not delivered by TBA; under 18 years of age; non-resident in community
2	TBAs	TBA role not confirmed by village head; unwilling to participate in study; under 18 years of age
3	Health Workers	Not involved in postnatal care delivery; unwilling to participate in study; under 18 years of age

Randomized Controlled Trial

We will exclude TBAs that plan to relocate over the intervention duration, who cannot be contacted via mobile phone, and who are not confirmed by community leadership. We will also exclude TBAs that do not provide informed consent for the entire study protocol including agreeing to have their delivery clients contacted to verify deliveries.

**4.6. Describe study procedures**

### Focus Group Discussions

The study will involve approximately 60-minute group discussions with 6-10 TBA delivery clients, TBAs, and health care providers separately. The discussions will be scheduled at the participant's convenience and to hold prior to the start of the randomized controlled trial. These discussions will be moderated by a trained qualitative researcher in the local implementing partner organization, Health Policy Research Group, using semi-structured discussion guides. An audio recording of the discussions and hand-written notes will also be made by another member of the local study team. Following transcription of audio recording to Microsoft Word of the discussions, all recordings and participation sheets with identifiers will be destroyed. Data analysis will involve de-identified data. Quotes by respondents will be identified by labels as follows: gender, age, occupation, e.g. Female, 40 years, Midwife. Focus group discussions will be held in quiet, secluded community spaces pre-identified with the help of community leaders in the language preferred by the majority of discussants – English or Igbo language. The choice of location will depend on the community leadership and participant preferences. We will ask for secluded and quiet spaces in selected communities that are options for meeting places. We will then sample opinions among discussion participants for the option that is most convenient for majority of participants. We will also make photo and video records of brief (~2min) segments of the discussions for presentation purposes.

The focus group discussions will collect the following data:

- i. From TBA delivery clients:
  - Perceived need for postnatal care
  - Understanding of community postnatal care norms – provider, location, timing, content
  - Perceived barriers and enablers of postnatal care attendance
  - Perception of the TBA role across the continuum of maternal care – from the antenatal to postnatal period
  - Potential implications of both referrals and incentives for referrals on perception of TBA role
- ii. From TBAs:
  - Services provided in community – content, timing, client base
  - Motivation for service provision
  - Perception of service quality relative to formal health care providers
  - Relationship between TBAs and formal health care providers in community
  - Current participation in referrals across the continuum of maternal care
  - Perceived barriers and enablers to participation in referrals for postnatal care
  - Potential implications of incentives for referrals on program participation
- iii. From health care providers:
  - Perception of maternal and neonatal need for routine PNC
  - Understanding and practice of current PNC recommendations – timing, content, provider
  - Perception of TBA role across the continuum of maternal care
  - Relationship between TBA and health care providers in community
  - Perceived health worker factors that enable or act as barriers to TBA participation in identified roles

### Randomized Controlled Trial

The primary outcome for this study is the proportion of delivery clients each TBA successfully refers for postnatal care within 48 hours of delivery.

The team will conduct postnatal care observation surveys in potential study villages. We will select villages that meet the criteria outlined in Section 3.1.

At baseline, trained enumerators will interview TBAs and complete a survey over 60 minutes in a private location chosen by the TBA. The information collected will include demographic data, stated motivation for services, description of services provided, and social network of the TBAs. We will make photo recordings of these interactions (between TBAs and enumerators) for the purpose of presentation as described below.

All TBAs that participate in the study will receive the following:

- Information on the study aims (attached to submission), the need for postnatal care attendance, and verbal encouragement to refer delivery clients to postnatal care within 48 hours of childbirth
- Offer of two-weekly cumulative payouts of \$0.70 per reported delivery they take that is verified by client.
- Each TBA will be assigned an identification number (TBA ID) and randomized with 50-50 probability to the referral incentive or control arm.

TBAs randomized to the referral incentive arm will also receive an offer of two-weekly cumulative payouts of \$2.00 per successful referral of delivery clients to early postnatal care in a facility if it is verified by the client. Delivery clients are women who have given birth assisted by the TBA. Verification is described below.

Thus, the required follow-up surveys will be conducted every two-weeks, consisting of:

- Self-reported deliveries by TBAs obtained via SMS messages sent by TBAs to the study team. TBAs will be asked to send a text message after each delivery they oversee. TBAs will text the name and contact details (phone number and address) of clients delivered over the past two weeks. Two-weekly calls will also be made by the study team to the TBAs to ensure that all deliveries are reported. Data to be recorded includes TBA name as well as TBA delivery client name, phone number, and address.
- Calls to women who TBAs report they delivered (TBA delivery clients) – these calls will ascertain delivery by TBA, date of delivery, date and location of attendance of postnatal care (if attended), referral to postnatal care by TBA, incidence of delivery and postnatal complications. In these contexts, delivery of a child and where delivery occurs is often common knowledge. The TBA is often involved in the naming ceremony that holds soon after. The study team will nevertheless recruit TBAs who are willing to share this information and allow both TBAs and their clients to opt out of the study.
- For a random subset of mothers, we will back-check the facility attendance registers to confirm postnatal care attendance. We will attach approval for access to patient information as a modification.

The anticipated duration of the intervention is September 2016 to January 31, 2017.

As part condition for the receipt of one of the study grants (Women and Public Policy Program's Cultural Bridge Fellowship), the study coordinator will blog on field research activities related to both the focus group discussions and randomized controlled trials. These blogs will contain pictures of survey respondents or focus group participants, for which informed consent will be sought.

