## ***Proposed Empirical Models***

### ***1. Average effect of incentives on early PNC referrals***

I identify the intention-to-treat effect of incentives on the proportion of TBA deliveries referred for postnatal care within 48 hours of delivery (early PNC).

$$y_{ij} = \beta_0 + \beta_1 * T + X_{ij} + \varepsilon_{ij}$$

Where:

- $y_{ij}$  is proportion of delivery clients or neonates (all, with or without delivery complications) referred by TBA  $i$ , in village  $j$  for early PNC;
- $T$  is a dummy variable indicating if the TBA is in the treatment arm;
- $X_{ij}$  is a set of baseline TBA covariates;
- $\beta_1$  is the coefficient of interest and gives the average mean difference in proportion of TBA clients referred between the treatment and the control arm.

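### Recent postnatal referrals are not among the listed baseline topics or named in X, which forgoes some precision and a direct balance check

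*Protocol*

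**What the plan says.** **Outcome.** Protocol 4.6, in its part on the trial, defines the endpoint: "The primary outcome for this study is the proportion of delivery clients each TBA successfully refers for postnatal care within 48 hours of delivery".

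**Baseline.** The same section plans one 60-minute interview per TBA: "The information collected will include demographic data, stated motivation for services, description of services provided, and social network of the TBAs". Past or current postnatal referral is not listed.

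**Where referral practice is listed.** The Focus Group Discussions part of 4.6 gives the TBA group two separate topics, "Services provided in community" and "Current participation in referrals across the continuum of maternal care". That group has 6 to 10 members and is not the trial sample.

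**When outcome data start.** Section 4.6 describes outcome collection after the offers and the randomisation: "Thus, the required follow-up surveys will be conducted every two-weeks". By then every TBA in both arms has received "verbal encouragement to refer delivery clients to postnatal care within 48 hours of childbirth". No run-in is described. On the period: "The anticipated duration of the intervention is September 2016 to January 31, 2017".

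**Model.** SAP model 1 says only that X "is a set of baseline TBA covariates". Protocol 5.1 is equally general. Neither names a referral measure, and no stratification of the 50-50 allocation is stated.

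**The concern.** A TBA who already sends her clients for postnatal care would be expected to keep doing so. Her referral rate before the trial is therefore the natural first candidate for X. If it is not collected before the encouragement and the allocation, an uncontaminated value is hard to recover later, because follow-up in the control arm is itself follow-up under encouragement. The baseline facility surveys in Protocol 4.4 do not fill the gap: they are anonymised observations of visits, used to choose villages, and are not linked to a TBA.

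Two things are at stake. One is the precision that adjustment would buy. The other is a baseline table that could show directly whether the arms started out alike in referring.

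**Working it through.** **Inputs.** From Protocol 5.2: difference 0.20, SD 0.37 across TBAs, two-sided alpha 0.05, 90% power, minimum 160 TBAs (80 per arm), maximum 200. The correlation r between a baseline referral proportion and the outcome is not in the documents; 0, 0.3 and 0.5 are assumed.

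**1. The plan's own figure.** n per arm = 2 × (1.960 + 1.2816)² × 0.37² / 0.20² = 2 × 10.507 × 0.1369 / 0.04 = 71.9, so 72 per arm or 144 in total (146 with a t-test). The stated 160 is not reproduced exactly, but it errs on the safe side. It would equal 144 / 0.90, a 10% dropout allowance, though none is stated.

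**2. Unadjusted precision at 160.** SE = 0.37 × √(2/80) = 0.0585. Power = Φ(0.20/0.0585 − 1.960) = Φ(1.459) = 92.8%. At 200 TBAs power is 96.9%.

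**3. With a baseline referral covariate.** SE is multiplied by √(1 − r²):

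| r | SE at 160 | Reduction | Power at 160 | Difference detectable with 90% power | Total N for 90% power |
|---|---|---|---|---|---|
| 0 | 0.0585 | none | 92.8% | 0.190 | 144 |
| 0.3 | 0.0558 | 4.6% | 94.8% | 0.181 | 132 |
| 0.5 | 0.0507 | 13.4% | 97.7% | 0.164 | 108 |

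The relevant r is the correlation that remains after the other covariates in X. If motivation, services or social network already predict referring, the added gain is smaller.

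**4. Chance imbalance.** Assume that prior referring also has SD 0.37. At 160 TBAs its arm difference then has a 95% range of ±1.96 × 0.0585 = ±0.115. The part passed on to the unadjusted β1 is r × 0.115, which is ±0.034 at r = 0.3 and ±0.057 at r = 0.5.

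**5. Is that shift already in the confidence interval?** Yes. The unadjusted 95% half-width for β1 is also 0.115. At r = 0.3 the adjusted half-width is 1.96 × 0.0558 = 0.109, and √(0.034² + 0.109²) ≈ 0.115. The imbalance is one component of the sampling error that the unadjusted interval reports. Adjustment removes that component; leaving it in does not make the interval wrong.

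**The case against.** **The list is open.** The protocol gives broad topics and the questionnaire is not in the documents. Other sections show that the list is not item by item: Protocol 10.1 mentions questions on income from services. A reader might infer that no referral question exists. The documents support only that none is listed. The separate focus-group topics suggest that the authors do not count referral as part of services, but that carries wording from one instrument to another. It stands either way that no referral covariate is named in X.

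**Validity is untouched.** A reader might infer that chance imbalance in prior referring would bias β1, or could not be adjusted for at all. With individual 50-50 randomisation β1 is unbiased, and step 5 shows that its interval covers the imbalance. Other members of X may also adjust for it in part.

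**Power is enough.** A reader might infer that the trial is underpowered without this covariate. On the stated inputs it is not: 160 TBAs exceed the 144 required.

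**The gain may be small.** Recall over two months covers about 10 deliveries (5 per month). Encouragement then changes behaviour in both arms and payment changes it in one. If early referral was rare before the trial, the covariate has little spread. Protocol 14.1 also calls TBA self-report unreliable. Its stated reason is the incentives, and Protocol 9.5 says the TBA consent form omits the referral incentive. However, 10.1 has TBAs told that the research aims to raise postnatal care use, so socially desirable answers remain possible. All of this lowers r, and it stands as a limit on the benefit.

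**Aim (d).** A reader might infer that the heterogeneity analysis is compromised. The plan restricts moderators to binary proxies for social preferences and does not present prior referring as one, so nothing planned is lost.

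**Conclusion.** The point holds as a low-cost improvement. Recent postnatal referring is not among the listed baseline topics and is not named in X. As written, the primary model therefore goes without the covariate most likely to predict the outcome, and balance on it cannot be checked directly.

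At 160 TBAs the forgone gain is a 5–13% smaller standard error and about 2 to 5 points of power (92.8% to 94.8–97.7%). That rests on an assumed correlation of 0.3 to 0.5 and on the planning SD of 0.37. At a correlation near zero only the balance check would be gained. That prior referring is the strongest predictor is a reasonable expectation, not something the documents show.

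**What to change.** In the planned baseline interview, before the encouragement and before allocation, ask each TBA:

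1. how many women she delivered in the last two months;
2. how many of them she referred to a facility for postnatal care;
3. how many of those referred attended within 48 hours of delivery.

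The second and third items are both needed because the endpoint is a successful referral, and Protocol 4.6 records attendance and referral separately at follow-up. The answer to item 3 divided by the answer to item 1 mirrors the endpoint.

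Report this proportion by arm in the baseline table. Name it in the SAP as a covariate in X for the primary model, with a missing indicator for TBAs who had no recent delivery. If the questionnaire already has such items, only the reporting and the SAP change are needed. Use as a moderator for aim (d) is optional.

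The cost is a few minutes in a 60-minute interview and one named covariate. The downside is recall and social-desirability error. This lowers the gain but, because the answers are collected before allocation, does not bias β1.

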##### 4.4. List inclusion criteria

###### Focus Group Discussions

S/No	Group	Inclusion Criteria
1	TBA delivery clients	Mother beyond 42 days after culmination of first pregnancy, who have thus had the opportunity to choose to attend postnatal care given current policy recommendations; resident in community; was delivered by a TBA; willing to participate in study; over 18 years of age
2	TBAs	Resident in community; TBA role (on-formally trained, independent of health system, provider of pregnancy-related care) confirmed by village head; willing to participate in study

3	Health Workers	Involved in postnatal care delivery within formal health care system, precisely direct patient care; works in same community; willing to participate in study
---	----------------	---------------------------------------------------------------------------------------------------------------------------------------------------------------

Randomized Controlled Trial

TBAs will be identified as community-based providers of antenatal and/or delivery care, and who are non-formally trained. TBAs must be resident within the community, must not plan to relocate over the intervention duration, must be reachable via mobile phone, and will be identified in partnership with community leadership. They will be willing to participate fully in the study, including having their clients contacted to verify delivery details and postnatal care use.

All delivery clients of TBAs will be interviewed, that is women who gave birth assisted by TBAs (and reported by the TBA to the study team as described below).

We will conduct baseline surveys of facilities in potential villages in which the study will be conducted. These surveys will involve anonymized observations of random postnatal care visits to ascertain process quality of care received. Villages in which postnatal care is of adequate quality will be selected.

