### **14. Participant Privacy**

#### **14.1. Describe provisions to protect participants' privacy (their desire to control access of others to themselves, e.g., the use of a private interview room) and to minimize any sense of intrusiveness that may be caused by study questions or procedures**

Group and individual interviews will be conducted in a private place, at the participant's convenience.

In the randomized controlled trial, we will ask TBAs to give us the names, addresses, and phone numbers of clients they deliver on a two-weekly basis. Follow-up calls to these clients will involve eliciting consent for inclusion in the study and ascertaining that delivery and referral by the TBA occurred. That is, we obtain information on the primary outcome of the study through follow-up surveys with TBA clients. Self-reports by TBAs given the incentives offered are likely to be unreliable.

The procedure of informed consent will be non-coercive and conducted in the language of choice for both the TBA and her clients. In these settings, it is not generally private information that a woman was pregnant, where she lives, and that she has delivered, and where she delivered. However, we will allow both the TBA and her clients to opt out of the study at any point that they consider the study procedures intrusive. The TBA and her clients will be informed of this provision. As long as drop-out of the study is non-differential across arms and is not in high proportions, this will not affect our ability to estimate effects.

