**15.3. Indicate how research team members and/or other collaborators are permitted access to information about study participants**

Field enumerators will only have access to data when during collection. Only the Harvard study team will have access to the entire study data.

The field work manager requires access to identifiable information about traditional birth attendants to implement the intervention – providing rewards for postnatal care referrals. Thus traditional birth attendants will inform the study team on a two-weekly basis of deliveries taken. Follow-up of these clients to ascertain postnatal care referrals will form the basis for determining rewards.

**15.4. If future use of data, data sharing, i.e., required of NIH-funded studies using/generating large-scale human genomic data, or future open access, i.e., free availability and unrestricted use, of data is planned or likely, indicate how data will be shared/released.**

No directly identifiable information will be made available to anyone other than the PI and Harvard faculty collaborators. Data in which names of participants will be replaced with an ID code may be shared with other collaborators as permitted in the consent form.

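### The time at which a birth is reported into the denominator is left open and not listed for recording, so births first reported after the 48-hour window could enter selectively by outcome and by arm

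*Protocol*

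**What the plan says.** **Outcome.** Protocol 4.6: "The primary outcome for this study is the proportion of delivery clients each TBA successfully refers for postnatal care within 48 hours of delivery". The models in protocol 5.1 and SAP section 1 take this proportion over all of a TBA's delivery clients.

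**Who enters.** Protocol 4.4 limits the client sample to "women who gave birth assisted by TBAs (and reported by the TBA to the study team as described below". In practice the denominator is what the TBA reports.

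**When a birth is reported.** Protocol 4.6 gives two timings in adjacent sentences: "TBAs will be asked to send a text message after each delivery they oversee", then "TBAs will text the name and contact details (phone number and address) of clients delivered over the past two weeks". Section 14.1 has only the second: "we will ask TBAs to give us the names, addresses, and phone numbers of clients they deliver on a two-weekly basis". So does section 15.3: "traditional birth attendants will inform the study team on a two-weekly basis of deliveries taken". Section 4.6 adds a backstop: "Two-weekly calls will also be made by the study team to the TBAs to ensure that all deliveries are reported".

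**What is recorded.** The items that 4.6 lists for the report are the TBA's name and the client's name, phone number and address. The time of the report is not listed. The date of delivery comes later, from the call to the client.

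**Payment.** Both arms receive $0.70 per reported delivery that the client verifies. The incentive arm also receives $2.00 per verified successful referral to early postnatal care (4.6 and 16.2).

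**The concern.** A birth reported before its 48-hour outcome exists cannot be left out because of that outcome. A birth first reported afterwards can be. The text does not say which report registers a birth, how soon it must arrive, or whether births first named in the two-weekly call count in the same way.

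This matters because the value of a report depends on the outcome in one arm only. In the incentive arm an attender brings $0.70 + $2.00 = $2.70 and a non-attender $0.70. In the control arm each brings $0.70. Outright concealment is not needed: more care in reporting the better-paid births would be enough to raise the incentive-arm proportion.

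The planned checks do not reach this. Section 14.1 itself regards TBA self-reports as probably unreliable given the incentives, and answers this by calling clients. The client calls and the register back-check in 4.6 test attendance among women already reported. Neither can find a non-attender who was never reported, and the two-weekly call goes back to the TBA.

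**Working it through.** The documents give no figure for the share of births whose window has closed when they are reported, so there is none to reproduce. The plan's delivery rate, used below, does reproduce: 68,092 / 1,170 / 12 = 4.85 deliveries per TBA per month, stated as about 5 (protocol 5.2).

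**Step 1. Share of listed births past 48 hours.** Inputs: a 14-day round and a 2-day window (4.6). Assumptions: births spread evenly, list sent at the end of day 14.

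(14 - 2) / 14 = 12/14 = 0.857, about 86%.

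At 5 births a month, a round holds 5 x 12/26 = 2.3 births, of which 2.3 x 12/14 = 2.0 are past the window. No matching share can be computed for a text after each delivery, because that text has no deadline.

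**Step 2. Illustration of bias.** Nothing in the documents supplies these values; they are assumed. Let b be true early attendance, equal in both arms. Let m be the share of past-window non-attenders that incentive-arm TBAs leave out, with none left out in the control arm.

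Observed incentive-arm proportion = b / [b + (1 - b)(1 - m x 12/14)]

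Example, b = 0.30 and m = 0.20: 0.30 / [0.30 + 0.70 x (1 - 0.171)] = 0.30 / 0.880 = 0.341, a rise of 0.041 with no true effect.

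| True attendance b | m = 10% | m = 20% | m = 30% |
|---|---|---|---|
| 0.20 | +0.015 | +0.032 | +0.052 |
| 0.30 | +0.019 | +0.041 | +0.066 |
| 0.50 | +0.022 | +0.047 | +0.074 |

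**Step 3. Scale.** The target difference is 0.20 (protocol 5.2), so the range is 0.0147/0.20 = 7% to 0.074/0.20 = 37% of it. With the plan's SD of 0.37 and 80 TBAs per arm, the standard error of the difference is 0.37 x sqrt(2/80) = 0.0585. The shift is then 0.015/0.0585 = 0.26 to 0.074/0.0585 = 1.27 standard errors. Under a normal approximation, a two-sided 5% test would reject a true null about 6% to 24% of the time.

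**Step 4. What a wholly false 0.20 would take.** If any non-attender could be left out, the share needed is 1 - b(1 - o) / [o(1 - b)], with o = b + 0.20. This is 62.5% for b = 0.20 and 57.1% for b = 0.30 or 0.50. If only past-window non-attenders could be left out, divide by 12/14: 73% and 67%.

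**The case against.** **The two timings can be read as one procedure.** A text after each birth, contact details each fortnight and a catch-up call fit together, and 4.6 introduces them as parts of a two-weekly follow-up. Sections 14.1 and 15.3 deal with privacy and data access and may only summarise that cycle. A reader might infer a flat contradiction; the text supports no more than an unresolved ambiguity. Section 9.5 says that client contact details are collected through follow-up survey tools, which are not in the documents and may be more exact. The items listed for recording are also introduced as a non-exhaustive list. This stands, but the protocol still names no registering report and no deadline.

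**Omission costs the TBA money.** Payment is per birth, not per proportion. Leaving out a verifiable non-attender gains nothing and forfeits $0.70 in either arm, and the calls exist to recover missed births. This stands and argues against large omission. It does not remove the difference between $2.70 and $0.70 in one arm only.

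**The TBA may not know the outcome.** A reader might infer that she knows it for 86% of the births she lists. The documents do not establish that: 86% is the share whose window has closed. Section 16.1 leaves her method open. A TBA who escorts the client would know; one who sends a message might not. Section 10.1 does expect TBAs to notice disparities in what clients report, which implies some knowledge, but not in every case.

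**Conclusion.** The concern holds as a gap in the reporting rule and in the data kept. The TBA's own report decides who enters the denominator, its timing is left open, and report time is not listed for recording. If that time is not kept, prompt and late reports cannot be separated afterwards.

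The 86% rests on even births and a list sent on day 14. The range of +0.015 to +0.074 rests wholly on assumed omission and attendance, gives the two-weekly calls no effect and confines omission to the incentive arm. It shows that modest selective reporting could matter against a target of 0.20, not that it will occur. A false effect of the full 0.20 would need most non-attenders to be left out.

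A reader might also infer that the sentence asking for a text after each delivery already brings this bias to zero. It does not. Without a deadline, that text may come on day 3 or day 10, and births added at the call still enter after their outcome. A deadline shrinks the route rather than closing it, since some clients will have attended before the text is sent.

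This is a worthwhile, low-cost improvement, not a ground for calling the trial invalid.

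**What to change.** **Protocol.** Reconcile 4.6, 14.1 and 15.3 to one rule: one text per birth, by a stated deadline inside the 48-hour window (24 hours is one option). Keep the SMS time and compare it with the delivery date from the client call. As that call records a date and not an hour, a text received no later than the calendar day after delivery can be counted as surely within 48 hours. Keep the two-weekly call as a catch-up, and flag births first named there as late.

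**SAP.** Keep the primary model on all reported births. Prespecify, by arm, the share of births reported late and the number of reported births per TBA. Add a sensitivity analysis with the same model on births texted before 48 hours, reported beside the primary result.

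**No automatic switch.** It is tempting to let the promptly texted births decide the conclusion if the two estimates differ. That rule would depend on the data, and it would condition on behaviour that follows randomisation and may respond to the incentive. It would also depart from the stated aim of covering all of a TBA's delivery clients.

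**Cost.** Some protocol wording, a small reporting burden on TBAs, a timestamp to retain and one more model run. The sensitivity subset is less precise, is not fully protected by randomisation, and may lose TBAs who have no on-time texts.
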